Month 6	XXX	XX.X ± XX.X (xx, xx)	XXX	XX.X ± XX.X (xx, xx)	0xxxx
Month 7	XXX	XX.X ± XX.X (xx, xx)	XXX	XX.X ± XX.X (xx, xx)	0xxxx
Month 8	XXX	XX.X ± XX.X (xx, xx)	XXX	XX.X ± XX.X (xx, xx)	0xxxx
Month 9	XXX	XX.X ± XX.X (xx, xx)	XXX	XX.X ± XX.X (xx, xx)	0xxxx
Month 10	XXX	XX.X ± XX.X (xx, xx)	XXX	XX.X ± XX.X (xx, xx)	0xxxx
Month 11	XXX	XX.X ± XX.X (xx, xx)	XXX	XX.X ± XX.X (xx, xx)	0xxxx
Month 12	XXX	XX.X ± XX.X (xx, xx)	XXX	XX.X ± XX.X (xx, xx)	0xxxx
Month 18	XXX	XX.X ± XX.X (xx, xx)	XXX	XX.X ± XX.X (xx, xx)	0xxxx
Month 24	XXX	XX.X ± XX.X (xx, xx)	XXX	XX.X ± XX.X (xx, xx)	0xxxx
Month 30	XXX	XX.X ± XX.X (xx, xx)	XXX	XX.X ± XX.X (xx, xx)	0xxxx
Month 36	XXX	XX.X ± XX.X (xx, xx)	XXX	XX.X ± XX.X (xx, xx)	0xxxx

Note: Similar tables will be produced for GGT, lactate dehydrogenase (LDH), sodium, potassium, chloride, glucose (fasting at screening visit only), total, direct and indirect bilirubin, AST, ALT, albumin; blood urea nitrogen, calcium, creatinine, uric acid, alkaline phosphatase, and amylase.
Data source: 16.2.12 Listing of chemistry

Table 14.3.6.2.2 Change in total protein at each follow-up assessment

	Treatment				
	DFP+DFP		DFO+DFP		
Visit	N	Mean ± SD (Min, Max)	N	Mean ± SD (Min, Max)	P-value (T-test)
Month 1	XXX	xx.x ± xx.x (xx, xx)	XXX	xx.x ± xx.x (xx, xx)	0xxxx
Month 2	XXX	xx.x ± xx.x (xx, xx)	XXX	xx.x ± xx.x (xx, xx)	0xxxx
Month 3	XXX	xx.x ± xx.x (xx, xx)	XXX	xx.x ± xx.x (xx, xx)	0xxxx
Month 4	XXX	xx.x ± xx.x (xx, xx)	XXX	xx.x ± xx.x (xx, xx)	0xxxx
Month 5	XXX	xx.x ± xx.x (xx, xx)	XXX	xx.x ± xx.x (xx, xx)	0xxxx
Month 6	XXX	xx.x ± xx.x (xx, xx)	XXX	xx.x ± xx.x (xx, xx)	0xxxx
Month 7	XXX	xx.x ± xx.x (xx, xx)	XXX	xx.x ± xx.x (xx, xx)	0xxxx
Month 8	XXX	xx.x ± xx.x (xx, xx)	XXX	xx.x ± xx.x (xx, xx)	0xxxx
Month 9	XXX	xx.x ± xx.x (xx, xx)	XXX	xx.x ± xx.x (xx, xx)	0xxxx
Month 10	XXX	xx.x ± xx.x (xx, xx)	XXX	xx.x ± xx.x (xx, xx)	0xxxx
Month 11	XXX	xx.x ± xx.x (xx, xx)	XXX	xx.x ± xx.x (xx, xx)	0xxxx
Month 12	XXX	xx.x ± xx.x (xx, xx)	XXX	xx.x ± xx.x (xx, xx)	0xxxx
Month 18	XXX	xx.x ± xx.x (xx, xx)	XXX	xx.x ± xx.x (xx, xx)	0xxxx
Month 24	XXX	xx.x ± xx.x (xx, xx)	XXX	xx.x ± xx.x (xx, xx)	0xxxx
Month 30	XXX	xx.x ± xx.x (xx, xx)	XXX	xx.x ± xx.x (xx, xx)	0xxxx
Month 36	XXX	xx.x ± xx.x (xx, xx)	XXX	xx.x ± xx.x (xx, xx)	0xxxx

Note: Similar tables will be produced for GGT, lactate dehydrogenase (LDH), sodium, potassium, chloride, glucose (fasting at screening visit only), total, direct and indirect bilirubin, AST, ALT, albumin; blood urea nitrogen, calcium, creatinine, uric acid, alkaline phosphatase, and amylase.
Data source: 16.2.12 Listing of chemistry

Table 14.3.6.2.3 Shift table for total protein in abnormal range at baseline vs last assessment:
DFP+DFP group

		Last Assessment				
		n (%)	Low	Normal	High	P-value (McNemar's test)
Baseline	Low	xx (xx)	xx (xx)	xx (xx)	0xxxx	
	Normal	xx (xx)	xx (xx)	xx (xx)		
	High	xx (xx)	xx (xx)	xx (xx)		

Note: Similar tables will be produced for GGT, lactate dehydrogenase (LDH), sodium, potassium, chloride, glucose (fasting at screening visit only), total, direct and indirect bilirubin, AST, ALT, albumin; blood urea nitrogen, calcium, creatinine, uric acid, alkaline phosphatase, and amylase.
Data source: 16.2.12 Listing of chemistry

Table 14.3.6.2.4 Shift table for total protein in abnormal range at baseline vs last assessment: DFO+DFP group

		Last Assessment				
		n (%)	Low	Normal	High	P-value (McNemar's test)
Baseline	Low	xx (xx)	xx (xx)	xx (xx)	0xxxx	
	Normal	xx (xx)	xx (xx)	xx (xx)		
	High	xx (xx)	xx (xx)	xx (xx)		

Note: Similar tables will be produced for GGT, lactate dehydrogenase (LDH), sodium, potassium, chloride, glucose (fasting at screening visit only), total, direct and indirect bilirubin, AST, ALT, albumin; blood urea nitrogen, calcium, creatinine, uric acid, alkaline phosphatase, and amylase.
Data source: 16.2.12 Listing of chemistry

Table 14.3.6.3.1 HIV Antibody at each assessment

	Treatment				P-value (Fisher's exact test)
	DFP+DFP		DFO+DFP		
	N	Positive n (%)	N	Positive n (%)	
Baseline	xxx	xx (xx)	xxx	xx (xx)	0xxxx
Month 6	xxx	xx (xx)	xxx	xx (xx)	0.xxxx
Year 1	xxx	xx (xx)	xxx	xx (xx)	0.xxxx
Year 3	xxx	xx (xx)	xxx	xx (xx)	0.xxxx

Note: Similar tables will be produced for Hepatitis B and C.

Data source: 16.2.13 Listing of serology

Table 14.3.7.1 Female patients with positive pregnancy test during the study

	Treatment	
	DFP+DFP	DFO+DFP
Pregnancy test: Positive		
Patient ID	XXXXXX XXXXXX XXXXXX XXXXXX	XXXXXX XXXXXX XXXXXX XXXXXX

Data source: 16.2.14 Listing of pregnancy

Table 14.4.1 The number and percent of patients who had compliance $\leq 80\%$ or $\geq 120\%$ during the study

	Treatment				P-value (Fisher's exact test)
	DFP+DFP		DFO+DFP		
Compliance	N	Percent	N	Percent	
< 80%	xx	xx.x%	xx	xx.x%	0xxxx
> 120%	xx	xx.x%	xx	xx.x%	0xxxx

Data source: 16.2.19 Listing of compliance

Table 14.5.1 Overall mean of transfusional iron input (mg/kg/day) during the study

	Treatment				P-value (T-test)
	DFP+DFP		DFO+DFP		
	N	Mean \pm SD (Min, Max)	N	Mean \pm SD (Min, Max)	
Overall mean of transfusional iron input (mg/kg/day)	xxx	xx.x \pm xx.x (xx, xx)	xxx	xx.x \pm xx.x (xx, xx)	0xxxx

Data source: 16.2.26 Listing of transfusion information

Table 14.6.1 Overall mean of total daily dose

	Treatment				P-value (T-test)
	DFP+DFP		DFO+DFP		
	N	Mean \pm SD (Min, Max)	N	Mean \pm SD (Min, Max)	
Overall mean of total daily dose (mg/kg/day)	xxx	xx.x \pm xx.x (xx, xx)	xxx	xx.x \pm xx.x (xx, xx)	0xxxx

Data source: 16.2.24 Listing of exposure

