4.2 Inclusion Criteria

Patients will be eligible to enroll in study LA38-EXT if they meet all the following criteria:

- 1. Completed study LA38-0411
- 2. Females of childbearing potential must have a negative pregnancy test result at Visit 1. In addition, if applicable, they must:
 - Use an effective method of contraception according to local requirements, during the study and within 30 days following their last dose of study medication, OR
 - Have had a tubal ligation (supporting evidence required), OR
 - Have had a hysterectomy (supporting evidence required), OR
 - Participate in a non-heterosexual lifestyle, OR
 - Have a male sexual partner who has been sterilized (supporting evidence required)
- 3. Fertile heterosexual males and/or their partners must agree to use an effective method of contraception during the study and for 30 days following the last dose of study medication
- 4. All patients and/or their authorized legal representatives must provide signed and dated written informed consent prior to the first study intervention, and assent will be obtained from patients who are considered to be minors. Patients must be able to adhere to study restrictions, appointments, and evaluation schedules.

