7.2.1.2 Monitoring and Documenting of Adverse Events

AEs and SAEs that are related to the underlying medical condition for which the patient enrolled in the clinical trial will be recorded separately from others.

Patients will be instructed to report any AEs to the investigator or a delegate. In addition, the investigator will solicit information about the occurrence of AEs through open-ended, non-leading verbal questions such as:

- How are you feeling / How does your child seem to be feeling?
- Have you/ has your child had any medical problems since the last visit?
- Have you / has your child taken any new medications, other than those provided in this study, since the last visit?

Based on the patient's response to these questions, the investigator or delegate should ask additional questions relevant to the specific complaint, such as:

- How severe is/was the symptom?
- How often did the symptom occur?
- How long did the symptom last?

The patient should also be questioned about any previously reported AEs that have not resolved.

The investigator will evaluate all AEs for their relationship to the investigational product (Section 7.2.1.3), intensity (Section 7.2.1.4), and seriousness (Section 7.2.1.5), and will document any measures taken to address the event. There should be an attempt to establish a diagnosis of the AE based on signs, symptoms, and/or other clinical information. Wherever possible, a diagnosis should be documented, rather than the individual signs/symptoms. All information is to be clearly recorded in the source documents.

If the dosage of study drug is reduced or treatment is discontinued as a result of an AE, the circumstances leading to such reduction or discontinuation must be clearly documented.

All AEs must be followed until resolution, the condition stabilizes, the event is otherwise explained, or the patient is lost to follow-up. The investigator is responsible for ensuring that follow-up includes any supplemental investigations that are needed to elucidate the nature and/or causality of the AE as completely as possible. This may include additional laboratory tests or investigations, histopathological examinations, or consultation with other health care professionals.

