4 STUDY PROCEDURES

The procedures and assessments to be conducted at each study visit are shown in Table 1.

Table 1 Table of study procedures

Procedure	Visit 1 ¹	Blood Draws ²	Visit 2	Visit 3	Visit 4	Visit 5	Visit 6	Visit 7	Visit 8	Visit 9 or Early Termination
Week:	0		13	26	39	52	65	78	91	104
Informed consent/assent	X									
Eligibility criteria	X									
Prior and concomitant medications	X		X	X	X	X	X	X	X	X
Transfusion information (if applicable) ³	X	X	X	X	X	X	X	X	X	X
Serum pregnancy testing (if applicable) ⁴	X		X	X	X	X	X	X	X	X
Physical examination	X					X				X
Vital signs (including weight and height) ⁵	X		X	X	X	X	X	X	X	X
12-lead ECG	X					X				X
Contraceptive counseling	X		X	X	X	X	X	X	X	X
Serology	X									X
Hematology	X	X	X	X	X	X	X	X	X	X
Biochemistry ⁶	X			X		X		X		X
Serum ferritin	X		X	X	X	X	X	X	X	X
Urinalysis	X					X				X
Liver MRI	X					X				X
Cardiac MRI T2*	X					X				X

Procedure	Visit 1 ¹	Blood Draws ²	Visit 2	Visit 3	Visit 4	Visit 5	Visit 6	Visit 7	Visit 8	Visit 9 or Early Termination
Week:	0		13	26	39	52	65	78	91	104
Dose calculation/verify and adjust dose level	X		X	X	X	X	X	X	X	
Collect used and unused study medication			X	X	X	X	X	X	X	X
Dispense study medication	X		X	X	X	X	X	X	X	
Dispense patient diary card	X		X	X	X	X	X	X	X	
Review and collect diary card			X	X	X	X	X	X	X	
Adverse events	X		X	X	X	X	X	X	X	X

¹ Visit 1 of study LA38-EXT is also the final visit of study LA38-0411. It serves as the baseline visit for those patients who received deferoxamine in LA38-0411 and will now be receiving deferiprone for the first time. (For patients who received deferiprone in LA38-0411, the measures obtained at the baseline visit of the LA38-0411 study will be used as the baseline measures for LA38-EXT as well.)

² For Group 1, hematology testing is to be done monthly throughout the study. For Group 2, it is to be done weekly up to Visit 3 (Week 26), biweekly up to Visit 5 (Week 52), and monthly thereafter. At the quarterly site visits, this testing will be done as part of the routine procedures, and at the other time points it can be done at a local laboratory instead of at the site.

³ Record volume of blood that the patient received during the transfusion, and the mean hematocrit of the packed red blood cell units transfused

⁵ Females of childbearing potential only

⁵ Height will be measured only at Visits 1, 5, and 9

⁶ At Visits 1, 3, 5, 7, and 9, the blood sample must be drawn following a 10-hour fast

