6.1.2 Secondary Endpoints

The time points for the efficacy assessments are defined below. Since the baseline measures are by definition those taken prior to the start of deferiprone therapy, “baseline” is defined differently for the two groups, as follows:

- **Group 1:** For patients who received deferiprone in LA38-0411, the baseline visit of that study will be treated as the baseline visit of LA38-EXT as well. Thus, Week 0 of the extension study will be Year 1 (i.e., the completion of one year of deferiprone treatment), Week 52 will be Year 2, and Week 104 will be Year 3 of deferiprone treatment.
- **Group 2:** For patients who received deferoxamine in LA38-0411, the start of the extension study (Week 0) will be treated as the baseline visit. For this group, therefore, Week 52 will be Year 1, and Week 104 will be Year 2 of deferiprone treatment.

Efficacy endpoints for deferiprone therapy are provided below. For Group 1, the change from baseline to Year 1 is derived from study LA38-0411. For Group 2, there is no Year 3 of deferiprone treatment.

- The change from baseline to Year 1 (both groups; Group 1 data are from LA38-0411), from baseline to Year 2 (both groups), and from baseline to Year 3 (Group 1 only) in liver iron concentration (LIC), as measured by magnetic resonance imaging (MRI)
- The change from baseline to Year 1 (both groups; Group 1 data are from LA38-0411), from baseline to Year 2 (both groups), and from baseline to Year 3 (Group 1 only) in cardiac MRI T2*
- The change from baseline to Year 1 (both groups; Group 1 data are from LA38-0411 data), from baseline to Year 2 (both groups), and from baseline to Year 3 (Group 1 only) in serum ferritin
- Responder analysis, defined as the percentage of patients who show a $\geq 20\%$ decline from baseline in LIC or serum ferritin or a $\geq 20\%$ increase from baseline in cardiac MRI T2* at Year 1 (both groups; Group 1 data are from LA38-0411), at Year 2 (both groups), and at Year 3 (Group 1 only)

In addition to the above analyses, the change from baseline to end of LA38-041 for deferoxamine and the change from baseline to end of LA38-EXT for deferiprone in Group 2 will be compared. The purpose of this analysis is to assess if deferiprone could maintain or even further improve LIC and MRI T2* after the patients were switched therapy.

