Month 15	XXX	XX.X ± XX.X (xx, xx)	XXX	XX.X ± XX.X (xx, xx)	0xxxx
Month 18	XXX	XX.X ± XX.X (xx, xx)	XXX	XX.X ± XX.X (xx, xx)	0xxxx
Month 21	XXX	XX.X ± XX.X (xx, xx)	XXX	XX.X ± XX.X (xx, xx)	0xxxx
Month 24	XXX	XX.X ± XX.X (xx, xx)	XXX	XX.X ± XX.X (xx, xx)	0xxxx
Month 27	XXX	XX.X ± XX.X (xx, xx)	XXX	XX.X ± XX.X (xx, xx)	0xxxx

	Treatment				
	DFP+DFP		DFO+DFP		
Month 30	xxx	xx.x ± xx.x (xx, xx)	Xxx	xx.x ± xx.x (xx, xx)	0xxxx
Month 33	xxx	xx.x ± xx.x (xx, xx)	Xxx	xx.x ± xx.x (xx, xx)	0xxxx
Month 36	xxx	xx.x ± xx.x (xx, xx)	Xxx	xx.x ± xx.x (xx, xx)	0xxxx

Data source: 16.2.5 Listing of vital signs including height and weight

Table 14.3.3.2 Change in weight from baseline to last assessment

		Treatment		
		DFP+DFP	DFO+DFP	
	N	xxx	xxx	P-value (T-test)
Change in weight (kg) Mean \pm SD (Min, Max)	Baseline	xxx.x \pm xxx.x (xxx, xxx)	xxx.x \pm xxx.x (xxx, xxx)	0.xxxx
	Last assessment	xxx.x \pm xxx.x (xxx, xxx)	xxx.x \pm xxx.x (xxx, xxx)	0.xxxx
	Change at last assessment	xxx.x \pm xxx.x (xxx, xxx)	xxx.x \pm xxx.x (xxx, xxx)	0.xxxx

Data source: 16.2.5 Listing of vital signs including height and weight

Table 14.3.3.1 Height (cm) at each assessment

		DFP+DFP	DFO+DFP		
Visit	N	Mean \pm SD (Min, Max)	N	Mean \pm SD (Min, Max)	P-value (T-test)
Baseline	xxx	xxx \pm xxx (xxx, xxx)	xxx	xxx \pm xxx (xxx, xxx)	0xxxx
Month 6	xxx	xxx \pm xxx (xxx, xxx)	xxx	xxx \pm xxx (xxx, xxx)	0xxxx
Month 12	xxx	xxx \pm xxx (xxx, xxx)	xxx	xxx \pm xxx (xxx, xxx)	0xxxx
Month 24	xxx	xxx \pm xxx (xxx, xxx)	xxx	xxx \pm xxx (xxx, xxx)	0xxxx
Month 36	xxx	xxx \pm xxx (xxx, xxx)	xxx	xxx \pm xxx (xxx, xxx)	0xxxx

Data source: 16.2.5 Listing of vital signs including height and weight

Table 14.3.3.4 Change in height from baseline to last assessment

		Treatment		
		DFP+DFP	DFO+DFP	
	N	xxx	xxx	P-value (T-test)
Change in height (cm) Mean \pm SD (Min, Max)	Baseline	xxx.x \pm xxx.x (xxx, xxx)	xxx.x \pm xxx.x (xxx, xxx)	0xxxx
	Last assessment	xxx.x \pm xxx.x (xxx, xxx)	xxx.x \pm xxx.x (xxx, xxx)	0xxxx
	Change at last assessment	xxx.x \pm xxx.x (xxx, xxx)	xxx.x \pm xxx.x (xxx, xxx)	0xxxx

Data source: 16.2.5 Listing of vital signs including height and weight

Table 14.3.4.1 Concomitant medications

		Treatment	
	DFP+DFP (N=xxx)	DFO+DFP (N=xxx)	
	Exposure (patient-years): x.xx		Exposure (patient-years): x.xx
	Total Patients Reporting: xx		Total Patients Reporting: xx
Preferred Name	n Patients (%)		n Patients (%)
Ccccc	x (x.x)		x (x.x)
Ccccc	x (x.x)		x (x.x)
Ccccc	x (x.x)		x (x.x)
.....

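### Height and weight change to last assessment is pooled over minors and adults, which dilutes any growth effect, and the baseline for these tables is not settled

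*SAP*

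**What the plan says.** **Population.** Protocol 4.2 sets no age limits of its own. The first criterion is "Completed study LA38-0411", and the consent criterion adds that "assent will be obtained from patients who are considered to be minors". The adverse event questions in Protocol 7.2.1.2 include a form for parents: "How does your child seem to be feeling". The number and ages of minors are not given.

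**Analysis.** SAP section 17 has two shells, "Change in weight from baseline to last assessment" (Table 14.3.3.2, kg) and "Change in height from baseline to last assessment" (Table 14.3.3.4, cm). Each shows one mean, SD and range per group, with a t-test p-value. The SAP gives these tables no age stratum, age- and sex-standardised score, annualised rate or age covariate.

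**Baseline.** Footnote 1 to SAP Table 1 says of Visit 1 of the extension: "It serves as the baseline visit for those patients who received deferoxamine in LA38-0411 and will now be receiving deferiprone for the first time". For the other group, "the measures obtained at the baseline visit of the LA38-0411 study will be used as the baseline measures for LA38-EXT as well". SAP 6.1.2 repeats the rule for efficacy: in Group 2, "the start of the extension study (Week 0) will be treated as the baseline visit". Week 104 is therefore Year 3 for Group 1 and Year 2 for Group 2. Nothing in the SAP names the baseline for the height and weight change tables in particular.

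**The concern.** The primary objective is long-term safety, and growth is a safety question only in patients who are still growing. Centimetres gained mean little in a child unless set against age, sex and elapsed time, and adults add patients whose expected height change is about zero. The pooled mean therefore shrinks any effect on growth, while the mixture of growers and non-growers widens the SD.

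If the two groups are also followed for different lengths of time, the t-test partly compares years of growth. It can then signal a difference where there is none, or cancel a real one. Weight has the same problem of interpretation: a child's expected gain and an adult's gain or loss are averaged together.

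**Working it through.** The documents state no effect size, SD, alpha or power for height or weight, so there is no figure to reproduce. Everything below is an illustration for height; nothing was computed for weight.

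**Inputs**
- From the documents: 300 planned at 2:1 (Protocol 1.2), so at most 200 and 100 enter the extension. Extension heights are taken at Visits 1, 5 and 9 only (SAP 5.2.5.2).
- Assumed: 150 v 75 patients analysed, all completing; the same share of minors *f* in both groups; every minor growing at *g* = 4-6 cm/year (between-child SD 1.5 cm/year); adults at zero; measurement SD 1 cm; two-sided 5% t-test.

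**1. Dilution (any baseline)**

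Pooled difference = *f* × difference in growing patients. Take 4 v 5 cm/year over an equal 2 years, a 2.0 cm deficit.

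- Minors only: SD = √((1.5×2)² + 1²) = √10 = 3.16 cm. With 30 v 15 minors (*f* = 20%), SE = √(10/30 + 10/15) = 1.00 cm. With 60 v 30 (*f* = 40%), SE = √(10/60 + 10/30) = 0.71 cm.
- Pooled: the variance in a group is *f*[(1.5×2)² + (2*g*)²] − (2*fg*)² + 1. At *f* = 20% this is 13.04 for *g* = 4 and 18.8 for *g* = 5, so SE = √(13.04/150 + 18.8/75) = 0.58 cm against a difference of 0.4 cm. At *f* = 40% it is 19.96 and 28.6, so SE = 0.72 cm against 0.8 cm.

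Power of the t-test by simulation:

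| Share of minors | Pooled difference | Power, pooled | Power, minors only |
|---|---|---|---|
| 20% | 0.4 cm | about 12% | about 50% |
| 40% | 0.8 cm | about 23% | about 80% |

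With 200 v 100 patients and a between-child SD of 2 cm/year, a normal approximation gives 8%, 12%, 17% and 31% pooled against 24%, 43%, 58% and 80% in growing patients only, at *f* = 10%, 20%, 30% and 50%. Restricting the table gains power despite the smaller numbers.

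**2. Which baseline?**

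Evidence for the written rule (3 v 2 years):
- Footnote 1 to SAP Table 1 covers the whole procedures table, including height and weight.
- The ECG shells print NA for the p-value at Months 6 and 36, as expected if Group 2 starts at Visit 1 of the extension.

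Evidence for a common LA38-0411 baseline (3 v 3 years):
- The height-by-visit shell has Month 6 and Month 36 rows with p-values for both groups. A scheduled Month 6 height in Group 2 can only come from LA38-0411.
- The weight-by-visit shell has monthly rows to Month 12 for both groups, although extension weight is quarterly.
- The baseline height shell has a footnote about separate screening visits, which the extension does not have.
- The LIC shell for the DFO+DFP group labels its extension data as Year 1 to Year 3.

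**3. Consequence of each baseline, no drug effect**

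Expected difference = *f* × *g* × (difference in years).

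| Share of minors | Expected difference, 3 v 2 years | Rejection, 3 v 2 | Rejection, 3 v 3 |
|---|---|---|---|
| 10% | 0.4-0.6 cm | 7-8% | about 5% |
| 20% | 0.8-1.2 cm | 17-20% | about 5% |
| 40% | 1.6-2.4 cm | 46-52% | about 5% |

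With 200 v 100 patients, SD 2 cm/year and 5 cm/year growth, rejection under 3 v 2 years is 11%, 24%, 40% and 77% at *f* = 10%, 20%, 30% and 50%. Unequal follow-up can also hide harm: 3.33 cm/year for 3 years equals 5 cm/year for 2 years (10 cm each), a difference of zero.

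**The case against.** The strongest reply is that the 3 v 2 year comparison is not established for these tables. SAP 6.1.2 defines time points for efficacy, and the by-visit height and weight shells fit a common LA38-0411 baseline. On that reading completers in both groups have 36 months and the over-rejection disappears. This stands, and a reader who infers that the p-value is certainly inflated goes further than the documents allow. It does not settle the matter, because footnote 1 and the ECG shells point the other way. The common baseline would also contradict footnote 1 and compare 3 years of deferiprone with 1 year of deferoxamine plus 2 of deferiprone.

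A reader might also infer that the groups differ in age mix. Nothing shows this. They come from a randomised trial, and the illustrations above give both the same share of minors. Selection into the extension could create an imbalance, since exclusion 2 applies to Group 2 only and exclusion 4 in practice to Group 1 only, but that is a possibility, not a finding.

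Nor do the documents support saying that a growth effect could not be seen at all. Power is reduced, not zero; the shells print minimum and maximum, and height and weight are listed by patient (listing 16.2.5).

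Finally, height and weight are not endpoints, and SAP section 17 says the shells show a general layout. That limits the weight of the point. But the shells are the only specification of this analysis.

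**Conclusion.** The point holds in two parts.

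- **Dilution is certain in direction under either baseline.** The pooled height effect is *f* times the effect in growing patients. Its size depends on the share of minors, which the documents do not give.
- **The baseline is unresolved, and the growth-time bias is conditional on it.** Over-rejection arises only under the written 3 v 2 year rule and is slight if few patients are minors. Under a common LA38-0411 baseline, rejection is nominal for completers, but the Group 2 change no longer describes deferiprone alone.

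The figures rest on assumed growth rates, SDs, group sizes and full completion. The power figures also concern a difference between groups. Counted from the start of deferiprone, both groups are on the drug throughout, so a deficit common to both would not show in any between-group test. This is a minor point about descriptive safety tables and leaves the primary endpoints untouched.

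**What to change.** In the SAP:

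1. State that the baseline for Tables 14.3.3.2 and 14.3.3.4 is the start of deferiprone in each group, and bring the by-visit height and weight shells into line.
2. Restrict the height-change table to patients under 18 at that baseline.
3. For these patients, report height-for-age and weight-for-age z-scores, naming the growth reference, or annualised velocity, at Years 1 and 2 on deferiprone, which both groups reach.
4. Show adult weight change in a separate table.
5. Drop the between-group p-value on change to last assessment.

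The cost is SAP wording, a standard derivation and the choice of a growth reference. Age, sex, height and weight are already collected. The drawback is smaller numbers in the paediatric table.
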